5.2 Secondary objectives

- To compare the effectiveness of probiotics vs. placebo, taken in conjunction with antibiotics, on the duration and severity of AAD in care home SUs.
- To compare the effectiveness of the probiotics vs. placebo in reducing the incidence of *C. difficile*-associated diarrhoea (CDAD) in care home SUs.
- To evaluate *th*e impact of the probiotics on Quality of Life (QoL) in care home SUs.
- To evaluate the cost effectiveness of probiotics for AAD in care home SUs.

6 Study design

This is a phase III individually randomised, double-blinded, parallel group trial of probiotic versus placebo for care home SUs who are prescribed antibiotics for acute infection. A total of 400 SUs from approximately 24 care homes in Wales (and potentially England) will be randomised.

The target population are SUs resident in care homes under a long-term care plan. Data entry, management and analysis will be conducted centrally at the South East Wales Trials Unit (SEWTU).

7 Centre and Investigator selection

Care homes located in Wales and if necessary from the South West and other parts of England will be approached to take part in the PAAD Study. We will seek agreement about participation in the study from the manager and the owner of suitable care homes. An agreement, detailing roles and responsibilities will be signed by the care home manager and the owner of the care home. The care home manager will be defined as the Principal Investigator (PI) at the care home, as the study site, and by Cardiff University as the sponsor of the study.

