14.4 Sample size

A total of 400 SUs (200 per arm) will need to be randomised in order to achieve 80% power, at the 5% level, to detect a 50% relative reduction in the incidence of antibiotic associated diarrhoea in those given probiotic intervention alongside antibiotic treatment, compared to placebo alongside antibiotic treatment. This sample size has been adjusted for a 20% loss to follow-up/withdrawal.

Taking into consideration the results from the interim analysis performed in PAAD Stage 1 and a more recent interim assessment of antibiotic prescribing and AAD (from first antibiotic prescription), assuming an AAD incidence of 25% in the placebo arm (lower confidence limit quoted in Appendix 3), in order to randomise 400 SUs we will need to obtain advanced consent from at least 607 SUs (assuming 66% will be prescribed at least one course antibiotics during the 12 month monitoring period and subsequently randomised) and will need to approach approximately 1214 SUs in order to achieve this consent rate (assuming only 50% will provide consent). With an average of 60 SUs per home, we will need to recruit from a minimum of 21 care homes. In order to allow for care home drop-out, larger than anticipated withdrawals/drop-out/declines and smaller than anticipated care homes, we aim to recruit from 24 care homes.

15 Analysis

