15.1.1 Secondary analyses

In a similar way to the primary analysis, a logistic regression model will be constructed, with 'Returned positive stool sample for *Clostridium difficile* toxin A and B following AAD' (YES/No) as the dependent variable and study arm (probiotic/placebo) as an explanatory variable, in order to investigate the effect of probiotics on the development of CDAD during the eight week follow-up period. In an analogous way to the primary, this analysis will adjust for clustering (if present) and confounding factors.

Generalised linear models will be used to order to:

- Investigate the effect of probiotics on the duration, frequency and recurrence of AAD during the eight week follow-up period
- Investigate the effect of probiotics on all-cause hospitalisations during the eight week follow-up period
- Investigate the effect of probiotics on illness recovery
- Investigate the effect of probiotics on antibiotic adherence
- Investigate the relationship between study intervention adherence and AAD/CDAD
- Investigate the relationship between antibiotic adherence and AAD/CDAD
- Investigate the effect of probiotics on mortality in the eight week follow-up period
- Investigate the effect of probiotics on both all-cause and AAD-related hospitalisation during the eight week follow-up period

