Proceed	There were no episodes of AAD lasting longer than two weeks. Of the 34 diagnostic stool samples received and analysed, 8 (24%) were found to have C. difficile . There we no episodes of AAD that resulted in bosnitalisation or death	The proportion of antibiotic prescriptions resulting in at least one episode of AAD is less than 18% and the proportion of AAD episodes classed as severe is low	Severe AAD*

Appendix 2 – Summary of analysis relating to stopping rules from stage 1 (observational study) to stage

+ Severe AAD is defined as AAD that (any of the following): lasts for more than two weeks, results in hospitalisation or death, is attributed to C.difficile.

* Presented as the raw proportion with confidence interval adjusted for clustering of prescriptions within service users. The most conservative estimate is presented here (removing episodes that correspond to service users who normally have loose stools and either have them 3+ times or day or a frequency that was unknown). † Severe AAD is defined as AAD that (any of the following): lasts for more than two weeks, results in hospitalisation or death, is attributed to C.difficile. PAAD Stage 2 RCT Protocol, Version 4.1, 07/09/2012

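### The CDAD analysis is tied to a covariate-adjusted logistic model, multilevel if clustering is present, although the protocol's planning figures imply only about 14 CDAD events

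*Protocol*

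**What the plan says.** CDAD is a named secondary objective in section 5.2: "To compare the effectiveness of the probiotics vs. placebo in reducing the incidence of" CDAD in care home residents. Section 14.3 defines a case as AAD followed by a diagnostic stool sample containing toxin A or B.

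Section 15.1.1 prescribes a logistic regression with study arm as an explanatory variable, modelled on the primary analysis, and adds: "In an analogous way to the primary, this analysis will adjust for clustering (if present) and confounding factors". The model it points back to is in section 15.1. That model is multilevel, to allow for residents clustered within care homes, and includes pre-specified confounding or risk factors whose list is left to the SAP. The clustering term is therefore conditional for CDAD. The covariate adjustment is not.

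No expected CDAD count appears anywhere. The inputs for one do:

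- Section 14.4: "A total of 400 SUs (200 per arm) will need to be randomised"; the design is to "detect a 50% relative reduction in the incidence of antibiotic associated diarrhoea", "assuming an AAD incidence of 25% in the placebo arm"; "This sample size has been adjusted for a 20% loss to follow-up/withdrawal"; about 24 homes.
- Appendix 2 (Stage 1 interim results): "Of the 34 diagnostic stool samples received and analysed, 8 (24%) were found to have" C. difficile.

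**The concern.** A logistic model needs enough events to carry its terms. The primary outcome has them, with about 60 AAD cases expected. CDAD is a subset of AAD, so carrying the same structure across asks far fewer events to support the same number of terms plus a between-home variance.

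Three things are at stake. The fit may fail through separation on a covariate or through non-convergence. With many covariates the odds ratio may move away from the null. If the prescribed model fails and nothing has been fixed in its place, the model that is reported will be chosen with the data in view. CDAD is clinically the most serious form of the outcome, so its estimate will be read closely even though it is secondary.

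**Working it through.** **The plan's own figure.** Two-sided 5%, 80% power, 25% against 12.5%:

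- Without continuity correction: 152 per arm; 152/0.8 = 190; total 380.
- With continuity correction: 168 per arm; 168/0.8 = 210; total 420.
- The stated 400 lies between these. With 20% loss, 200 × 0.8 = 160 per arm remain, giving 82% power for AAD. The primary sample size is sound.

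**Expected CDAD events** = analysed residents × AAD risk × C. difficile share of AAD samples:

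- Placebo: 160 × 0.25 × 8/34 = 9.4
- Probiotic: 160 × 0.125 × 8/34 = 4.7
- Total: 14.1 among 320 residents

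**Sensitivity, using figures in the protocol:**

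| Change from the base case | Expected events |
|---|---|
| Share 20% or 30% (section 4.1.3) | 12.0 or 18.0 |
| No loss, 200 per arm | 17.6 |
| No treatment effect | 18.8 |
| AAD 34% (Stage 1 point estimate) | 19.2 |
| AAD 34% and share 30% | 24.5 |
| No loss, AAD 42%, no effect, share 30% | 50.4 |

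The exact 95% interval for 8/34 is 11% to 41%, which is 6 to 25 events out of 60 AAD cases. About 12 to 25 is a reasonable working range. The last row stacks every favourable assumption.

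**Spread over homes.** 14.1/24 = 0.59 events per home. Under a Poisson approximation with homes of equal size, 24 × exp(−0.59) ≈ 13 homes have no event and about 3 have two or more. There is little from which to estimate a home-level variance, or to judge whether clustering is present.

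**Terms against events.** Study arm, a home variance and two covariates (an assumed minimum) make four parameters: 14.1/4 ≈ 3.5 events per parameter.

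**Precision of the simplest comparison.** Risks are 0.25 × 8/34 = 5.9% and 0.125 × 8/34 = 2.9%. The odds ratio is (4.71 × 150.59)/(9.41 × 155.29) = 0.48. SE of the log odds ratio = √(1/9.41 + 1/4.71 + 1/150.59 + 1/155.29) = 0.58, so the expected 95% interval is about 0.16 to 1.50. Power for a true halving is 16% by Fisher's exact test and 25% by the normal approximation.

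**Behaviour of the adjusted model.** Single-level logistic fits were simulated at 160 per arm with a true odds ratio of 0.485. The number and prevalence of binary covariates were assumed, because the protocol does not list them.

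- The median treatment odds ratio stayed at 0.45 to 0.49, and 95% intervals covered the truth about 97% of the time.
- Separation or non-convergence: about 1.5% with arm alone, about 1–2% with common covariates, and roughly 15–33% with several uncommon ones.
- With eight covariates the estimate drifted modestly away from the null.
- Firth fits with arm alone had no failures and a slightly smaller spread.

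The random intercept was not simulated, so these failure rates do not include any difficulty from the home-level term.

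**The case against.** The strongest reply is that the protocol leaves the covariate list to the SAP and makes the clustering term conditional, so the size of the CDAD model is not fixed here. A reduced model or convergence rule for rare events is ordinary SAP content, and the SAP was not available for this review. This stands in part: the degree of overfitting cannot be known, and the SAP may already hold a fallback. But section 15.1.1 itself commits CDAD to the covariate-adjusted model, and that commitment can be judged against the protocol's own event count.

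A second reply is that most fits would succeed and the treatment estimate would be close to the truth. That stands, and it limits the claim. A reader might infer that the model cannot be estimated or will probably give an exaggerated odds ratio. The simulations do not show this for a modest set of covariates.

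Other stronger readings also lack support:

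- That 17.6 events is a ceiling. It holds only at 25% AAD, a full halving and the Stage 1 share of 8/34.
- That toxin-positive cases can only equal or fall below the Stage 1 share. Section 4.2 describes cultures and section 14.3 requires toxin, so a lower count is plausible. But 8/34 is a share of samples, and a resident may have several episodes or a second sample.
- That one third of AAD cases would yield no sample, because 34 samples stand beside 51 prescriptions with AAD. Those figures come from an interim cut of an ongoing study and are not shown to be the same cases.
- That the protocol wrongly claims power for CDAD. It claims power only for AAD, so labelling the CDAD comparison as estimation only is a reporting preference.

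**Conclusion.** The point holds in limited form. Section 15.1.1 carries a covariate-adjusted logistic model, multilevel if clustering is present, over to an outcome for which the protocol's inputs imply about 14 events, with about 12 to 25 plausible. That is too few to support a home-level variance and several covariates. The harm is a material risk of a failed or unstable fit, from about 1–2% up to roughly a third of fits depending on covariates, together with a modest drift of the odds ratio when many are included. It is not a demonstrated large bias.

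The event count rests on 25% placebo AAD, a halving, 20% loss and the Stage 1 share of 8/34. The failure rates rest on assumed covariates in single-level fits. The outcome is secondary, and this is an inexpensive improvement worth making.

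**What to change.** In section 15.1.1, replace the adjusted CDAD model with a pre-specified Firth penalised (or exact) logistic regression having study arm as the only fixed term. Report it with the raw counts in each arm and a risk difference with an interval suited to small numbers. State that any covariate- or cluster-adjusted CDAD model is supportive only.

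Because residents are randomised individually, an arm-only comparison is valid without confounder adjustment. The change takes about two sentences and needs no new data. Its price is that the main CDAD estimate no longer adjusts for covariates or for clustering by home. If the SAP already holds an equivalent rule, section 15.1.1 needs only to be brought into line with it.

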11.3 Dose modification for toxicity

If bloating is experienced, it is recommended to reduce the daily intake to half to allow for adjustment. If the participant continues to be uncomfortable the study medication should be stopped.

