13.4.1 Daily Diary

A diary will be kept for an eight week follow-up period. The diary will record information on adherence to the study intervention over the 21 day period and for the antibiotic treatment period; study adverse events and symptoms related to diarrhoea severity and illness severity.

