14.1 Randomisation

Randomisation will be carried out using random permuted blocks. Computer-generated random numbers will be produced to select a block of allocations from the set of all possible permutations of allocations (on a 1:1 ratio) given a particular block-size before the trial begins.

14.2 **Primary outcome measures**

The primary outcome is the occurrence of at least one episode of AAD during the eight weeks following randomisation. AAD is defined as three or more loose stools (defined as a 5 – 7 on the BSC) in a 24 hour period following a period of normal stool consistency.

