14.3 Secondary outcome measures

- The occurrence of *C.difficile*-associated diarrhoea (CDAD). This is defined as having a diagnostic stool sample (following the occurrence of AAD) that is found to contain *Clostridium difficile* toxin A or B.
- Health-related quality of life measured using the EQ-5D.
- The duration, frequency and recurrence of AAD. The duration of AAD is defined as the total number of consecutive 24 hour periods that a SU has AAD (as per our definition in 14.2.).
- The frequency of AAD is the number of episodes of AAD a SU experiences during the eight week follow-up period. AAD episodes are only considered unique if they are separated by a period of at least three days of "normal" stool consistency
- Recovery from the illness that triggered the prescription of antibiotic treatment. A single item will be asked daily and will capture the illness severity of the SU on a particular day
- Adherence to the study intervention and antibiotic treatment. Adherence will be defined as full (all doses on a particular day), partial (at least one dose but not all) and not (no doses on a particular day).
- Healthcare Resource Use. Costs will incorporate information on GP and practice nurse consultations, other medication, procedures, investigations, hospital appointments, A&E attendances and any hospital inpatient admissions and will be measured at the end of the eight-week follow-up period.
- Unplanned (not a routine hospital appointment) hospitalisation, both all-cause and AAD-related.

- Adverse events. These include reported symptoms such as vomiting, abdominal pain, excessive flatulence, bloating, skin rashes.
- All-causes mortality during the eight week follow-up period.

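### The planned regressions of AAD/CDAD on adherence do not require adherence to come before the diarrhoea, so diarrhoea that leads residents to stop sachets can look like a benefit of full adherence

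*Protocol*

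**What the plan says.** Section 15.1.1 opens its list with "Generalised linear models will be used to order to" and includes two adherence items: "Investigate the relationship between study intervention adherence and AAD/CDAD" and "Investigate the relationship between antibiotic adherence and AAD/CDAD". No time ordering, lag or landmark is attached to either.

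The windows are set elsewhere:
- **Sachet adherence** (13.4.1): "The diary will record information on adherence to the study intervention over the 21 day period". The CRF schedule (Table 1) has adherence completed daily in weeks 1 to 4.
- **AAD** (14.2): "The primary outcome is the occurrence of at least one episode of AAD during the eight weeks following randomisation".
- **CDAD** (14.3): "This is defined as having a diagnostic stool sample (following the occurrence of AAD") and testing positive for toxin A or B.
- **Adherence score** (14.3): "Adherence will be defined as full (all doses on a particular day), partial (at least one dose but not all"), or none.

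Section 10.1 lets the investigator withdraw a resident from the intervention when a change in condition justifies it, or for intolerance. Section 11.3 says of bloating that "it is recommended to reduce the daily intake to half to allow for adjustment", and that sachets stop if discomfort continues. Section 15.1 bases the primary analysis on intention to treat.

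**The concern.** Adherence is measured after randomisation, and for a resident whose AAD starts during the course, part of it is measured after the outcome has occurred. If diarrhoea prompts staff or the resident to stop the sachets, the outcome has produced the low adherence. A model with AAD as response and whole-course adherence as predictor reads this backwards: poor adherers show more AAD, and full adherence appears to protect. This can happen in either arm, including placebo. The antibiotic item has the same structure.

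At stake is the reading of a secondary analysis. If the randomised comparison is null, an apparent benefit among good adherers could be taken as evidence that the product works when taken properly.

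There is also a smaller scoring problem. The regimen is one sachet twice a day (11.1). A resident on the halved intake of 11.3 takes one sachet of two. Read literally, 14.3 scores that day as partial, although 11.3 was followed.

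**Working it through.** **Windows.** The adherence window is days 1 to 21 and the AAD window is days 1 to 56. The first lies wholly inside the second. Only AAD with onset in days 1 to 21 can cause stopping within the course.

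**Plan's own figure.** The protocol gives none for this analysis. Evaluable residents: 400 × (1 − 0.20) = 320 (14.4).

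**Null model.** Neither probiotic nor adherence affects AAD. Assumptions, none given by the protocol:
- 15% of residents stop for unrelated reasons, on a day spread evenly over days 1 to 21.
- A share *s* of AAD begins in days 1 to 21, evenly spread. *s* = 21/56 = 0.375 corresponds to even onset over eight weeks; 0.60 and 0.80 represent earlier onset.
- A fraction *q* of those residents stop at onset.
- Adherent means at least 80% of 21 days, so at least 17 days taken. Stopping on day 17 or earlier makes a resident non-adherent.

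**Formulas.**
- Non-adherent without AAD: u = 0.15 × 17/21 = 0.1214.
- Non-adherent with AAD: v = u + s × (1 − u) × q × 17/21.
- Odds ratio for AAD, adherent versus not: OR = [(1 − v)/v] ÷ [(1 − u)/u], where (1 − u)/u = 7.235.

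The overall AAD risk cancels, so the 25% placebo risk in 14.4 does not drive the result.

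**Example** (s = 0.60, q = 0.25): v = 0.1214 + 0.60 × 0.8786 × 0.25 × 0.8095 = 0.2281. OR = (0.7719/0.2281) ÷ 7.235 = 0.47.

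| Share of AAD in days 1–21 | q = 0 | q = 10% | q = 25% | q = 50% |
|---|---|---|---|---|
| 0.375 | 1.00 | 0.80 | 0.60 | 0.40 |
| 0.60 | 1.00 | 0.70 | 0.47 | 0.27 |
| 0.80 | 1.00 | 0.64 | 0.39 | 0.20 |

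Simulation with 25% AAD agrees to within about 0.01. A second simulation, with exponential onset within 56 days, gives about 0.67, 0.47 and 0.36 at 10, 20 and 30% stopping when median onset is 14 days. With a 7-day median it gives 0.58, 0.39 and 0.27.

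**False findings.** With 320 evaluable residents and clustering ignored, a significant protective association appears in about 3 to 5% of simulated trials with no AAD-driven stopping, 11 to 26% at 10%, 35 to 83% at 25% and 78 to 100% at 50%.

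**Does time order remove it?** Restricting to residents free of AAD at day 21, with later AAD as outcome, gives odds ratios of 0.98 to 1.02 in every scenario of the table.

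**Does truncation remove it?** Counting adherence only to the day before first AAD gives cases a shorter window. Under the null with exponential onset (medians of 14 and 7 days), defining adherence as 80% of pre-onset days gives an odds ratio of about 1.6 to 2.4. Requiring 17 pre-onset days gives about 0.03 to 0.08. Both errors appear even with no AAD-driven stopping.

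**Complier-average effect.** This is the arm difference in AAD risk divided by the arm difference in the proportion reaching the adherence threshold on active product. With no effect of arm the numerator is about zero, so the estimate is about zero whatever the stopping pattern.

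**The case against.** The strongest reply is that the protocol does not fix the regression criticised. Section 15.1.1 gives one line per item. It does not state how daily adherence is summarised, which variable is the response, or the time window. It speaks of a relationship for adherence, and of an effect for the randomised comparisons. Daily records make a time-ordered analysis possible, and a statistical analysis plan not shown here may specify one. This stands in part: the bias is a risk the text leaves open, not a certainty. But the items sit among effect analyses with no descriptive label, and nothing in the protocol orders adherence before AAD.

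Several stronger readings are tempting and should not be drawn:
- *That adherence and AAD cover the same period.* They overlap; 21 days lie inside 56.
- *That full adherence will look beneficial.* This depends on how often AAD leads to stopping. The protocol gives no rate and does not name diarrhoea as a reason to stop. Sections 10.1 and 11.3 only make the route possible.
- *That the antibiotic item must be biased towards protection.* It was not simulated, and antibiotics themselves cause AAD (4.1.1), so its net direction is not settled.
- *That reduced-intake days will be commoner on active.* Section 4.1.6 says mild to moderate gastrointestinal side effects are generally no more common than on placebo.
- *That 14.3 certainly scores such days as partial.* That is its literal sense, but neither section says which intake counts as all doses.

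It is also fair that these are secondary items and that their use to reinterpret a null result is conjecture.

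**Conclusion.** The concern holds as a risk that the protocol leaves open. Relating AAD to whole-course sachet adherence, without requiring adherence to come first, can produce a protective association when there is no effect. The odds ratio is roughly 0.6 to 0.8 if 10% of residents with AAD during the course stop because of it, and 0.3 to 0.6 at 25 to 30%. With no such stopping it is 1.0. These sizes rest wholly on assumed onset timing, stopping fractions, 15% unrelated stopping and an 80% cut-off. The direction for sachets rests only on the overlap of the windows and on some AAD-driven stopping. The intention-to-treat primary analysis and the sample size of 400 are not touched. The change is worth making, but it does not bear on the validity of the main result.

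**What to change.** 1. **Study-intervention adherence.** Replace the regression in 15.1.1 with a complier-average causal effect analysis: randomised arm as instrument, all randomised residents included, adherence threshold set in advance. The cost is a wider interval. With 87.9% reaching the threshold (1 − 0.1214, from the assumptions above), it is about 1/0.879 = 1.14 times as wide as that for the intention-to-treat risk difference. The method also assumes that arm acts on AAD only through reaching the threshold, which should be stated.
2. **Antibiotic adherence, and any adherence association still reported.** Randomised arm is not a valid instrument for antibiotic adherence, because antibiotics are not randomised and arm may affect AAD directly. Use a landmark analysis (residents free of AAD at the end of the adherence window, later AAD as outcome) or time-varying adherence, and label it descriptive. The landmark loses events: of 320 × 0.25 = 80 AAD cases, 50 remain if 37.5% start during the course and 16 if 80% do.
3. **Do not simply cut adherence off at the day before first AAD**, for the reason shown in the working.
4. **Reconcile 14.3 with 11.3**, so that it is clear whether a day on the reduced intake is scored full or partial.

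This needs a few sentences in 14.3 and 15.1.1 and modest programming. Adherence and stools are already recorded daily, so no new data and no change to treatment are required.
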